3.2 Secondary Objectives and Endpoints

For the secondary objectives, we will compare treatment and control arms based on the following list of clinical endpoints which capture different aspects of disease severity.

OBJECTIVES	ENDPOINTS (OUTCOME MEASURES)

1. Evaluate the clinical efficacy of convalescent plasma administration by comparing treatment vs control arms
 
 • Clinical Severity 
 ○ Ordinal scale: 
 ■ Time to recovery, defined by time to levels 1-3 on the ordinal scale ■ Time to an improvement of one category and two categories from Day 1 using an ordinal scale. ■ Participant clinical status using ordinal scale at Days 3, 5, 8, 11, 15, 22, and 29. ■ Mean change in the ordinal scale from Day 1 to Days 3, 5, 8, 11, 15, 22, and 29. 	
 • Clinical outcome assessed using ordinal scale daily while hospitalized and on Day 15, 22, and 29. • Clinical status assessment (8-point ordinal scale) includes: 
 1. Not hospitalized, no limitations on activities. 2. Not hospitalized, limitation on activities and/or requiring home oxygen; 3. Hospitalized, not requiring supplemental oxygen - no longer requires ongoing medical care; 4. Hospitalized, not requiring supplemental oxygen - requiring ongoing medical care (COVID-19 related or otherwise); 5. Hospitalized, requiring supplemental oxygen; 6. Hospitalized, on non-invasive ventilation or high flow oxygen devices; 7. Hospitalized, on invasive mechanical ventilation or ECMO; 8. Death

 ○ National Early Warning Score (NEWS): 
 ■ Time to discharge or to a NEWS of ≤ 2 and maintained for 24 hours, whichever occurs first ■ Change from Day 1 to Days 3, 5, 8, 11, 15, and 29 in NEWS. 	
 • NEWS assessed daily while hospitalized and on Days 15 and 29.

 ○ Oxygenation: 
 ■ Oxygenation free days to Day 29. ■ Incidence and duration of new oxygen use during the study. 	
 ■ Days of supplemental oxygen (if applicable)

OBJECTIVES	ENDPOINTS (OUTCOME MEASURES)

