5 STUDY POPULATION

5.1 Inclusion Criteria

1. Adult ≥ 18 years of age
2. Laboratory-confirmed SARS-CoV-2 infection as determined by PCR or other authorized or approved assay in any specimen collected within 72 hours prior to enrollment.

Note – An exception must be requested to the Sponsor if ≥ 72 hours since positive test.

3. Hospitalized in participating facility.
4. Documentation of pneumonia with radiographic evidence of infiltrates by imaging (e.g., chest x-ray or CT scan).
5. Abnormal respiratory status that is judged worse than baseline by the investigator and as documented at any point within 24 hours prior to randomization, consistent with ordinal scale levels 5, 6 or 7, specifically defined as:
 - Room air saturation of oxygen (SaO_2) $< 93\%$, OR
 - Requiring supplemental oxygen, OR
 - Tachypnea with respiratory rate ≥ 30
6. Patient or proxy is willing and able to provide written informed consent and comply with all protocol requirements

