8.1.4 National Early Warning Score (NEWS)

NEWS has demonstrated an ability to discriminate participants at risk of poor outcomes. (Smith, 2016). This score is based on 7 clinical parameters (see [Table 1](#)). The NEWS is being used as an efficacy measure. This should be evaluated at the first assessment of a given study day and prior to administration of study product. The 7 parameters can be obtained from the hospital chart using the last measurement prior to the time of assessment and a numeric score given for each parameter (e.g., a RR of 9 is one point, oxygen saturation of 92 is two points). This is recorded for the day obtained. i.e., on Day 3, Day 3 score is obtained and recorded as Day 3.

Table 1: National Early Warning Score (NEWS)

PHYSIOLOGICAL PARAMETERS	3	2	1	0	1	2	3
Respiration Rate	≤8		9 - 11	12 - 20		21 - 24	≥25
Oxygen Saturations	≤91	92 - 93	94 - 95	≥96			
Any Supplemental Oxygen		Yes		No			
Temperature	≤35.0		35.1 - 36.0	36.1 - 38.0	38.1 - 39.0	≥39.1	
Systolic BP	≤90	91 - 100	101 - 110	111 - 219			≥220
Heart Rate	≤40		41 - 50	51 - 90	91 - 110	111 - 130	≥131
Level of Consciousness				A			V, P, or U

Level of consciousness = alert (A), and arousable only to voice (V) or pain (P), and unresponsive (U).

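### The secondary time-to-NEWS endpoint (discharge, or NEWS ≤2 held for 24 hours) can already be met at Day 1 by some eligible participants, who then count as early events without improving

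*Combined protocol and SAP*

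**What the plan says.** - **Endpoint.** Section 3.2 lists "Time to discharge or to a NEWS of ≤ 2 and maintained for 24 hours, whichever occurs first" under clinical efficacy. The synopsis (1.1) repeats it, and section 3.3 uses it for the exploratory comparison with recipients of active drug in an external protocol. Section 8.1.4 confirms the role of the score: "The NEWS is being used as an efficacy measure".
- **Entry.** Inclusion criterion 5 in section 5.1 asks for abnormal respiratory status "documented at any point within 24 hours prior to randomization, consistent with ordinal scale levels 5, 6 or 7". It then gives three alternatives: room air saturation below 93%, "Requiring supplemental oxygen, OR" respiratory rate of 30 or more. Any one is enough, and no minimum NEWS is set.
- **Scoring.** In Table 1 the item "Any Supplemental Oxygen" scores 2 for yes and 0 for no, whatever the device or flow.
- **Timing.** Section 8.1.4 says of the daily score: "This should be evaluated at the first assessment of a given study day and prior to administration of study product". The Day 1 value is therefore taken before plasma. NEWS is collected daily in hospital, then on Days 15 and 29.
- **Analysis.** Section 9.4.3 plans cumulative incidence curves for time-to-event endpoints, with death as a competing risk, compared by Gray's test or, for a cause-specific hazard ratio, the log-rank test. It contains no rule for participants already at or below the threshold on Day 1 and leaves further detail to the SAP. The text available for this review contains no such rule.

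**The concern.** A time-to-improvement endpoint should start from a state in which the event has not yet happened. Here the entry criteria and the event definition overlap. A participant who enters at the threshold and stays there is recorded as reaching the favourable outcome within a day or two, in either arm, whatever the treatment does.

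Two things are at stake. The first is sensitivity: such events carry no information on treatment, shorten the median time in both arms and reduce power. The second is meaning: because the oxygen item ignores device and flow, an alert participant who is stable on low-flow oxygen (ordinal level 5), or in principle on high-flow oxygen (level 6), is counted with participants who went home. The ordinal improvement endpoint in the same section is anchored to change from Day 1. The NEWS event is not.

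**Working it through.** **Step 1. Check the reading of Table 1.** Section 8.1.4 gives two worked examples: "a RR of 9 is one point, oxygen saturation of 92 is two points". Scoring respiratory rate 9 and saturation 92 from the table gives 1 and 2, so the reading reproduces the plan's own figures.

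**Step 2. Score eligible profiles.** Item order: respiratory rate, saturation, oxygen, temperature, systolic pressure, heart rate, consciousness.

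| Profile (all else in the zero column) | Sum | NEWS | ≤2? |
|---|---|---|---|
| On oxygen, alert | 0+0+2+0+0+0+0 | 2 | yes |
| Room air, saturation 92 | 0+2+0+0+0+0+0 | 2 | yes |
| On oxygen, saturation 94–95 | 0+1+2+0+0+0+0 | 3 | no |
| On oxygen, heart rate 91–110 | 0+0+2+0+0+1+0 | 3 | no |
| On oxygen, respiratory rate 21–24 | 2+0+2+0+0+0+0 | 4 | no |
| On oxygen, not alert | 0+0+2+0+0+0+3 | 5 | no |
| Room air, saturation 91 or less | 0+3+0+0+0+0+0 | 3 | no |
| Room air, respiratory rate 30 or more | 3+0+0+0+0+0+0 | 3 | no |

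Across all category combinations on oxygen, exactly one reaches ≤2: every other item at zero. The first row enters by the oxygen alternative of criterion 5, the second by the room-air alternative. The qualifying status need only have been present at some point in the previous 24 hours, so it may also have eased by the time Day 1 is scored.

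**Step 3. Date the event.** If the pre-dose Day 1 score can start the 24 hours and the Day 2 score is still ≤2, the event falls on Day 1 (onset) or Day 2 (confirmation). If only later scores count, it falls at about Day 2 to 3. The plan does not say which applies. Either way no improvement is needed.

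**Step 4. Size under the planned type of test.** The share f already at the threshold is an assumption. Also assumed: 40 per arm, exponential times with means 12 and 6 days (hazard ratio 2), follow-up to Day 29, no deaths (so the log-rank test stands in for Gray's test), two-sided 0.05.

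- Event probabilities by Day 29: 1 − exp(−29/12) = 0.911 and 1 − exp(−29/6) = 0.992, which sum to 1.903.
- With k = 40f baseline-met participants per arm, informative events D = (40 − k) × 1.903, with information I = D/4.
- The tied block of 2k early events adds variance but no signal: V = 2k × 0.25 × (80 − 2k)/79.
- Power ≈ Φ(ln 2 × I/√(I + V) − 1.96).

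| f | D | I | V | Approximate power | Simulated log-rank power |
|---|---|---|---|---|---|
| 0 | 76.1 | 19.03 | 0 | 0.86 | about 0.83 (0.83–0.85) |
| 10% | 68.5 | 17.13 | 1.82 | 0.78 | about 0.78 (0.77–0.81) |
| 20% | 60.9 | 15.22 | 3.24 | 0.69 | 0.67–0.70 (0.67–0.71) |
| 30% | 53.3 | 13.32 | 4.25 | 0.60 | 0.59–0.60 (0.57–0.63) |

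The ranges in brackets are the spread over separate simulation runs and ways of treating ties.

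**Step 5. Cross-check from the plan's own power figure.** Section 9.2 states about 80% power for 0.50 against 0.80 with 40 per arm. With the usual two-proportion formula, power = Φ((0.30√40 − 1.96√(2×0.65×0.35))/√(0.25+0.16)) = Φ((1.897 − 1.322)/0.640) = Φ(0.90) = 0.816, so the stated figure is reproduced. Replacing each rate p by f + (1 − f)p gives 0.55 against 0.82 (power 0.748) at f = 10%, 0.60 against 0.84 (0.672) at 20%, and 0.65 against 0.86 (0.591) at 30%. The losses are of the same order.

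**The case against.** The case for leaving the endpoint alone has several parts.

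- **Few may be affected.** Only one combination on oxygen qualifies, it must last 24 hours, and participants are meant to be severely ill with pneumonia. Sedated ventilated participants score at least 5. A participant at 92% on room air may soon be given oxygen and then score differently. All of this stands. The documents give no baseline NEWS distribution, so the share could be near zero, and the 10–30% values are only illustrations.
- **The consequences are limited.** This is one of many secondary endpoints in a phase 1 trial with mainly descriptive analyses, and section 9.4.3 names survival and time to recovery as the key ones. Other listed endpoints cover change in NEWS from Day 1, ordinal improvement and days free of oxygen support. This stands and limits the weight of the point.
- **Detail is left to the SAP.** True, but the event definition is a stated rule. As written it counts unchanged participants as successes, so this is more than missing detail.

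Stronger readings are tempting and should be resisted. A reader might apply a rank-sum test to the event times, which in the same scenario gives a fall from about 75% to about 20% at f = 30%. Section 9.4.3 reserves the rank-sum test for continuous endpoints, and the planned type of test loses much less. A reader might also infer that participants on oxygen generally meet the endpoint at entry. Table 1 does not support that. Finally, a reader might think it enough to require the oxygen item to be 0. It is not: the participant at 92% on room air would still qualify unchanged.

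**Conclusion.** The point holds as a statement of what the definition permits. By two routes, an eligible participant can be at the NEWS threshold on Day 1 and become an event at about Day 1 to 3 without improving. The scoring is certain. The number of participants affected is unknown and may be small.

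If the share were 10%, 20% or 30%, power under a log-rank or Gray-type test would fall from about 83% to about 78%, 67–70% and 59–60%. This rests on an assumed hazard ratio of 2, 40 per arm, no deaths, and equal shares in both arms. The effect is dilution and harder interpretation. It does not favour either arm, because the Day 1 score precedes plasma and randomisation balances the share on average. The primary efficacy ranking uses ordinal levels 1–3 for recovery and does not use NEWS, so it is not affected. The change is worth making because it is cheap, but it does not threaten the trial's main result.

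**What to change.** In sections 1.1 and 3.2 and in the SAP:

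1. Count the NEWS component only from assessments after Day 1, and state that two consecutive daily scores are needed for the 24 hours.
2. For participants with Day 1 NEWS ≤2, count only discharge as the event. This closes both the oxygen and the room-air route and keeps every randomised participant in the analysis.
3. Require the supplemental-oxygen item to be 0 at the qualifying assessments, so that a participant still on oxygen is not counted with those discharged.
4. Keep the current definition as a supportive analysis and for the external comparison in section 3.3, and report by arm how many participants had Day 1 NEWS ≤2.

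The cost is a few sentences. All seven NEWS items are already recorded daily in hospital, so no new data are needed and care does not change. The one drawback is that the main definition would no longer match the one listed for the external comparison, which is why the current version is kept for that purpose.

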
 ○ Non-invasive ventilation/high flow oxygen: 
 ■ Non-invasive ventilation/high flow oxygen - free days to Day 29. ● Incidence and duration of new non-invasive ventilation or high flow oxygen use during the study. 	
 ● Days of non-invasive ventilation (if applicable). ● Days of high flow oxygen (if applicable).

 ○ Invasive Mechanical Ventilation / extracorporeal membrane oxygenation (ECMO): 
 ■ Ventilator / ECMO free days to Day 29. ■ Incidence and duration of new mechanical ventilation or ECMO use during the study. 	
 ● Days of invasive mechanical ventilation (if applicable). ● Days of ECMO (if applicable).

 ● Hospitalization 
 ○ Duration of hospitalization. 	
 ● Days of hospitalization

 ● Mortality 
 ○ Survival Time ○ 14-day mortality ○ 28-day mortality 	
 ● Date and cause of death (if applicable)

2. Evaluate the safety of convalescent plasma plus standard care vs. standard of care alone by:
 
 ● Cumulative incidence of Grade 3 and 4 clinical and/or laboratory AEs through Day 29. ● Changes in WBC with differential, hemoglobin, platelets, creatinine, glucose, total bilirubin, ALT, AST, and PT over time (analysis of lab values in addition to AEs noted above). 	
 ● SAEs ● Grade 3 and 4 AEs ● WBC with differential, hemoglobin, platelets, creatinine, glucose, total bilirubin, ALT, AST, and PT on Day 1; Days 3, 5, 8, and 11 (while hospitalized); and Days 15 and 29 (if attends in-person visit or still hospitalized).

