Cumulative incidence curves will be considered for time-to-event endpoints, treating death as a competing risk. Gray's test, or if the cause-specific hazard ratio was of interest the log-rank test, will be used to compare groups. Binary proportions will be estimated along with Clopper-Pearson 95% confidence intervals and compared between arms using Fisher's exact test. Continuous endpoints will be summarized with means, SD and normal 95% confidence intervals; Wilcoxon rank-sum will be used to compare arms for continuous endpoints. Ordinal endpoints (e.g. 8-point clinical severity score) will be summarized by their multinomial proportions across the different categories at Study Day 15,

22 and 29. An exact Mann-Whitney test will be used to test for whether the ordinal clinical severity was higher in one arm versus the other for ordinal endpoints. Further details for the analysis of secondary endpoints will be provided in the Statistical Analysis Plan.

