9.4.8 Tabulation of Individual Participant Data

The time course of participants clinical and laboratory markers will be considered. Frequency of evaluation varies across clinical and laboratory assessments. Adverse event and clinical evaluation will occur daily while individual is in hospital and otherwise include Day 15, 22, 29, and 60. Laboratory measures will generally occur at days 3, 5, 8 and 11 while participant is in hospital. The full list of evaluations are shown in the Schedule of Activities (Appendix 12.1).

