12 APPENDIX

12.1 Schedule of Activities (SoA)

The following page outlines all of the assessments to be conducted during the study. A detailed presentation of assessments immediately follows the table.

Table 4: Schedule of Activities

	Screen	Baseline	Study Period				
	While inpatient			While inpatient or as outpatient visits			
Day +/- Window	-1 or 1	1	Day 2 to 29	15 ⁷ ± 2	22 ⁷ ± 3	29 ⁷ ± 3	60 ⁷ ± 5 ¹⁰
ELIGIBILITY							
Informed consent	X						
Demographics & Medical History	X						
Targeted physical exam	X						
Review SARS-CoV-2 results	X						
STUDY INTERVENTION							
Randomization		X					
Administration of investigational plasma		X					
STUDY PROCEDURES							
Vital signs including SpO ₂		X ⁴	Daily until discharge or Day 29 of hospitalization	X		X	X
Clinical data collection ¹		X ⁴	Daily until discharge or Day 29 of hospitalization	X	X ⁸	X	X
Targeted medication review		X ⁴	Daily until discharge or Day 29 of hospitalization	X		X	X
Adverse event evaluation		X ⁴	Daily until discharge or Day 29 of hospitalization	X	X	X	X
SAFETY LABORATORY							
Type and Screen	X ^{2,3}						
Safety hematology, chemistry and liver tests		X ^{4,5,6}	Day 3, 5, 8, 11 (all ± 1 day) if hospitalized ^{5,6}	X ⁹		X ⁹	
Pregnancy test for females of childbearing potential	X ^{2,3}						
RESEARCH LABORATORY							
Oropharyngeal swab or endotracheal sample		X ⁵	Day 3, 5, 8, 11 (all ± 1 day) if hospitalized	X			

Blood for research		X ⁵	Day 3, 8, (all ± 1 day)	X		X	X
--------------------	--	----------------	-------------------------	---	--	---	---

1 Refer to [Section 8.1](#) of the protocol for details of clinical data to be collected including ordinal score, NEWS, oxygen requirement, mechanical ventilator requirement, etc.

2 Screening laboratory tests include: ALT, AST, creatinine (and calculate an estimated glomerular filtration rate (eGFR)), and pregnancy test.

3 Laboratory tests performed in the 48 hours prior to enrollment will be accepted

4 Baseline assessments should be performed prior to study drug administration. Laboratory tests performed as part of routine clinical care in the 24 hours prior to first dose will be accepted for the baseline safety laboratory tests. Baseline may be the same as the screening laboratory tests.

5 Safety laboratory tests include WBC with differential, hemoglobin, platelets, creatinine, glucose, total bilirubin, ALT, AST, and PT.

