6 Any laboratory tests performed as part of routine clinical care within the specified visit window can be used for safety laboratory testing. Window during the study period is ±1 day.

7 In-person visits are preferred but recognizing quarantine and other factors may limit the participant's ability to return to the site for the visit. In this case, these visits may be conducted by phone and blood and OP can be coordinated remotely.

8 Phone call at Day 22 is to assess clinical status (ordinal scale), adverse events, readmission to a hospital, and mortality only.

9 Safety laboratory tests on Day 15 and 29 if still hospitalized or returns to the site for the visit or at home visit.

10 The collection of Day 60 data for primary and secondary endpoints and the collection of Day 60 samples for exploratory tests may be performed up to 90 days following the Day 60 visit.

12.2 Division of AIDS (DAIDS) Table for Grading the Severity of Adult and Pediatric Adverse Events, Corrected version 2.1 (July 2017)

[Division of AIDS \(DAIDS\) Table for Grading the Severity of Adult and Pediatric Adverse Events \(Corrected Version 2.1 - July 2017\)pdf](#)

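### Detection of laboratory Grade 3-4 AEs depends on length of stay and attendance, and the crude pooled Day 29 comparison makes no allowance for this

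*Combined protocol and SAP*

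**What the plan says.** Section 3.2 lists as a secondary safety endpoint, plasma against standard care, "Cumulative incidence of Grade 3 and 4 clinical and/or laboratory AEs through Day 29". Section 8.4.1 counts an abnormal laboratory finding as a possible AE and captures every Grade 3 and 4 event.

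The safety laboratory schedule is conditional:

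- Section 3.2 sets the post-baseline panel at "Days 3, 5, 8, and 11 (while hospitalized); and Days 15 and 29 (if attends in-person visit or still hospitalized".
- The Schedule of Activities (12.1) has "Day 3, 5, 8, 11 (all ± 1 day) if hospitalized" for the early draws.
- Its footnote 9 has "Safety laboratory tests on Day 15 and 29 if still hospitalized or returns to the site for the visit or at home visit".
- Its footnote 7 says that, where in-person attendance is limited, "these visits may be conducted by phone and blood and OP can be coordinated remotely".
- Its footnote 6 adds "Any laboratory tests performed as part of routine clinical care within the specified visit window can be used for safety laboratory testing".
- Section 9.4.8 repeats the early pattern: "Laboratory measures will generally occur at days 3, 5, 8 and 11 while participant is in hospital".

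Clinical events are sought differently. AE evaluation is daily in hospital and then on Days 15, 22, 29 and 60, whether or not the participant has gone home.

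For analysis, section 9.4.3 says "Binary proportions will be estimated along with Clopper-Pearson 95% confidence intervals and compared between arms", using Fisher's exact test. Section 9.4.1 makes available-case analysis the default. Section 9.4.4 tabulates Grade 3 and 4 AEs by arm and calls the safety analysis mainly descriptive. No section deals with unequal numbers of blood draws.

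**The concern.** A Grade 3-4 laboratory value is recorded only if blood is taken. Someone discharged on Day 4 has one scheduled post-baseline draw before Day 15. Someone still in hospital has four, and probably routine-care bloods as well. Length of stay is a post-randomization outcome: section 2.3.2.1 hypothesizes that plasma will shorten illness, and section 3.2 lists duration of hospitalization as an endpoint. Death also ends the draws.

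If stays differ, the arms are searched for laboratory events with different intensity. A shorter stay on plasma would lower its observed laboratory rate at unchanged risk and could offset a real excess. A longer stay would do the reverse. Pooling with clinical events, which are sought at every contact, makes this hard to see in the published table. Safety is the trial's first aim, so the table will be read across arms even if no test is emphasized.

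**Working it through.** **The plan's own figure.** Table 3 (section 9.2) gives the only AE-detection probabilities. For 40 participants and a 4% rate, 1 − 0.96^40 = 0.805, matching the printed 0.80; all eight rows reproduce. The table assumes that every event is seen. If only half were detected, 4% would act like 2%, and the probability would be 1 − 0.98^40 = 0.55, the table's own 2% row.

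**Inputs from the documents.** Draw days 3, 5, 8 and 11 (inpatients only) and 15 and 29 (inpatient or attending); 40 per arm.

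**Assumptions, not document figures.** Exponential stay from Day 1, with median 12 days in one arm and 7, 9 or 10 in the other; risk p = 0.05 of a Grade 3-4 value at each draw, equal in both arms; attendance a = 0.5 at Days 15 and 29 after discharge; no deaths.

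**Expected scheduled draws.** The share still in hospital on Day d is 0.5^((d−1)/median). Days 15 and 29 contribute share + a × (1 − share).

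| Median stay | Day 3 | Day 5 | Day 8 | Day 11 | Day 15 (with attenders) | Day 29 (with attenders) | Total |
|---|---|---|---|---|---|---|---|
| 12 | 0.891 | 0.794 | 0.667 | 0.561 | 0.723 | 0.599 | 4.24 |
| 10 | 0.871 | 0.758 | 0.616 | 0.500 | 0.689 | 0.572 | 4.01 |
| 7 | 0.820 | 0.673 | 0.500 | 0.371 | 0.625 | 0.531 | 3.52 |

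**Probability of at least one detected event, scheduled draws only.** For each discharge interval, detection = 1 − product of (1 − p) over certain draws and (1 − ap) over uncertain ones. Each value is weighted by the share of participants in that interval.

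| Discharged | Detection | Share, median 12 | Share, median 7 |
|---|---|---|---|
| before Day 3 | 0.049 | 0.109 | 0.180 |
| Days 3-5 | 0.097 | 0.097 | 0.147 |
| Days 5-8 | 0.142 | 0.126 | 0.173 |
| Days 8-11 | 0.185 | 0.106 | 0.129 |
| Days 11-15 | 0.226 | 0.116 | 0.121 |
| Days 15-29 | 0.246 | 0.247 | 0.188 |
| after Day 29 | 0.265 | 0.198 | 0.062 |

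The weighted sums are 19.2% and 16.2%, a ratio of 0.84 with identical true risk. For 12 versus 9 days the ratio is 0.92. For 12 versus 10 days it is 18.2/19.2 = 0.95.

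**Near-daily inpatient bloods.** The same formula with a draw on every inpatient day from Day 2 to Day 29 gives 45.9% for median 12, 35.1% for median 7 and 42.3% for median 10. The ratios are 35.1/45.9 = 0.76 and 42.3/45.9 = 0.92.

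**What could be hidden.** The per-draw excess that would show as no difference is roughly the ratio of draws: 4.24/3.52 = 1.20 for 12 versus 7 days, and 4.24/4.01 = 1.06 for 12 versus 10. Solving exactly for 12 versus 7 gives about 1.2 with scheduled draws and about 1.5 with daily draws.

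**Scale against sampling error.** 19.2% versus 16.2% is a 3-point gap. The 95% half-width for the difference is 1.96 × √(0.192×0.808/40 + 0.162×0.838/40) = 0.167, about 17 points.

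**Effect of restricting to Days 3, 15 and 29.** For 12 versus 7 days, expected draws are 0.891+0.723+0.599 = 2.21 and 0.820+0.625+0.531 = 1.98. The same interval weighting gives 10.65% and 9.56%, ratio 0.90. With full attendance it is [1 − 0.95²(1 − 0.820×0.05)] / [1 − 0.95²(1 − 0.891×0.05)] = 0.1345/0.1377 = 0.98. The restriction shrinks the bias without removing it.

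**The case against.** A reader might infer that scheduled blood draws stop at discharge. They do not: Days 15 and 29 remain on the schedule, home visits count, and remote blood collection is allowed. Only the Day 3 to 11 draws require an inpatient.

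A reader might also infer that the shorter-stay arm is bound to show fewer events and so hide toxicity. That needs a material difference in stay or early death, which the documents do not give. It also touches only the laboratory part of a composite, so the pooled figure moves less than the laboratory-only ratios above. The size depends mainly on the assumed difference in stay.

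The near-daily scenario is not specified either. Footnote 6 accepts routine-care bloods only within visit windows, which leave Days 18 to 25 uncovered, although section 8.4.4 lets AEs come to light through laboratory tests more generally. The model also gives every draw the same independent risk; a persistent abnormality missed on Day 8 could still be found on Day 15.

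The practical weight is limited. Section 9.2 calls AE analysis mainly descriptive for lack of power. Section 9.1 expects related events soon after infusion, when most participants are probably still inpatients. Section 3.2 separately plans an analysis of laboratory values over time and reports duration of hospitalization.

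These points reduce the severity and stand. None of them corrects the AE proportion for unequal numbers of draws.

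**Conclusion.** The point holds in conditional form. Laboratory Grade 3-4 AEs are ascertained according to length of stay, survival and attendance, and the planned crude Day 29 proportion ignores this. Under the assumptions above (median 12 versus 7 to 10 days, 5% per draw, 50% attendance), the spurious laboratory ratio is about 0.84 to 0.95 with scheduled draws and about 0.76 to 0.92 with near-daily inpatient bloods. If stays, early deaths and attendance are similar in the two arms, the bias largely disappears. It would also be small for toxicity that shows by Days 3 to 5. The documents do not support saying that laboratory toxicity will be hidden. They support saying that the pooled figure cannot be read across arms without knowing how many participants were tested, and when. This merits a change of reporting, not of design.

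**What to change.** In sections 3.2, 9.4.3 and 9.4.4, and in the SAP that section 9.4.1 promises:

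1. Report clinical and laboratory Grade 3-4 AEs separately by arm.
2. Tabulate laboratory Grade 3-4 events by scheduled window (Days 3, 5, 8, 11, 15, 29). Show the number tested, the number not tested because of discharge, death or a missed visit, total draws and inpatient days, all by arm.
3. Add a sensitivity comparison limited to protocol-scheduled draws on Day 3 and on Days 15 and 29, which are scheduled regardless of discharge. Show missing tests by arm beside it.
4. State that the pooled Day 29 proportion is descriptive and subject to unequal ascertainment.

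Day 3 alone should not become the headline. Under the assumed stays only 82% to 89% are still inpatients then, and later toxicity would drop out of the comparison. Events per draw should not be the main comparison either: the denominator is set after randomization and is dominated by sicker, longer-stay participants.

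The cost is one extra table and more cautious wording. No visit or procedure is added.
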